1.2.2. Known and Potential Benefits and Risks With Xanthine Oxidase Inhibitors

Subjects must be on a stable, medically appropriate dose of XOI, which are recommended as the first line treatment for hyperuricemia associated with gout ([Khanna 2012](#), [Zhang 2006](#)).

Allopurinol, approved in 1966 in the United States, is the most commonly used XOI. With allopurinol as a monotherapy, the most common AE is skin rash. Skin reactions may be severe and can be fatal. Other common AEs include diarrhea, nausea, and elevation in liver function tests (alkaline phosphatase, alanine aminotransferase [ALT], and aspartate aminotransferase [AST]). Furthermore, some allopurinol toxicities appear to be dose related, such as nausea, diarrhea, Stevens-Johnson syndrome, and toxic epidermal necrolysis ([Chao 2009](#), [Halevy 2008](#)).

Febuxostat, approved in 2009, is another XOI approved for the chronic management of hyperuricemia in patients with gout. The approved dosing in the US is 40 to 80 mg qd, and the approved dosing in the European Union (EU) is 80 to 120 mg qd. With febuxostat as monotherapy, a higher rate of CV thromboembolic events was seen in clinical studies, although a causal relationship has not been established. There have been reports of liver failure (some resulting in death) and rhabdomyolysis in patients taking febuxostat. Other AEs occurring in $> 1\%$ of febuxostat-treated patients included liver function abnormalities, nausea, arthralgia, and rash ([Uloric \[US package insert\] Rev March 2013](#), [Febuxostat 80 mg Tablets \[SmPC\] Rev December 2012](#)).

The local product label for allopurinol ([Allopurinol \[US package insert\] Rev July 2015](#), [Allopurinol 100 mg Tablets \[SmPC\] Rev February 2013](#)) and febuxostat ([Uloric \[US package](#)

insert] Rev March 2013, Febuxostat 80 mg Tablets [SmPC] Rev December 2012) should be consulted for detailed information regarding contraindications, warnings and precautions, drug interactions, dosage adjustment and patient monitoring recommendations, and use in special patient populations.

1.2.3. Known and Potential Benefits and Risks With Colchicine

As many as 80% of patients experience an acute gout flare with initiation or increase in dose of urate lowering therapy (ULT) (Borstad 2004). Per the American College of Rheumatology (ACR), European League Against Rheumatism (EULAR), and British Society of Rheumatology treatment guidelines, gout flare prophylaxis is recommended to reduce the potential for acute gout flares that can occur with the initiation of ULT (Khanna 2012, Zhang 2006). The EULAR guidelines note that evidence to support the use of low-dose colchicine for prophylaxis of acute attacks when beginning ULT is reasonable. As such, subjects in this study should take colchicine for gout flare prophylaxis during approximately the first 6 months on study.

Although generally well tolerated, low-dose colchicine has been associated with AEs such as diarrhea, abdominal pain, nausea, and vomiting. Rarely, more severe AEs such as myopathy, neuropathy, and myelosuppression have been reported with colchicine use. The local product label for colchicine should be consulted for detailed information regarding contraindications, warnings and precautions, drug interactions (eg, P-gp or strong/moderate CYP3A4 inhibitors, or 3-hydroxy-3-methyl-glutaryl-coenzyme A [HMG-CoA] reductase inhibitors, or digitalis glycosides, see Section 7.1.3), dosage adjustment and patient monitoring recommendations, and use in special patient populations. Subjects unable to tolerate or that have known contraindications to colchicine will have the option of taking low-dose oral corticosteroids for gout flare prophylaxis. This alternative is also recommended by the ACR treatment guidelines (Khanna 2012).

1.3. Rationale for Study Design and Dose Selection

The efficacy and safety of lesinurad 200 mg qd in combination with an XOI (allopurinol or febuxostat) were demonstrated in 3 pivotal Phase 3 studies. The Phase 3 studies included subjects with normal renal function and those with mild to moderate renal impairment (estimated creatinine clearance [eCrCl] ≥ 30 mL/min). Subjects with eCrCl < 30 mL/min were excluded. Among the limited number of subjects with moderate renal impairment (eCrCl 30 to < 60 mL/min; N=294), including those with eCrCl 30 to < 45 mL/min (N=84), lesinurad 200 mg in combination with an XOI demonstrated a consistent safety and efficacy profile irrespective of Baseline renal function of eCrCl ≥ 30 mL/min. Lesinurad 200 mg in combination with an XOI has been approved in the US and EU for the treatment of hyperuricemia associated with gout in patients who have not achieved target serum uric acid levels with an XOI alone.

This Phase 4 randomized, double-blind, placebo-controlled study is designed to provide additional safety and efficacy data with lesinurad 200 mg plus XOI in the important subgroup of subjects with gout and moderate renal impairment who have not achieved the target sUA level < 6.0 mg/dL on a medically appropriate dose of an XOI alone. Long-term safety, particularly renal safety, over a 24 month Treatment Period will be assessed. Eligible subjects are required to have an eCrCl 30.0 to < 60.0 mL/min and be on a stable, medically appropriate dose of XOI for at least 4 weeks prior to Screening and throughout the Screening Period with sUA levels above

target. The minimum Baseline dose of allopurinol permitted is 200 mg daily; the minimum Baseline dose of febuxostat is the lowest approved dose per the local product label. The maximum dose of each XOI permitted is the highest approved dose per the local product label. Eligible subjects will be randomized to receive lesinurad 200 mg (the dose approved by FDA and EMA) or placebo in combination with their prescribed XOI for up to 24 months. Per the ACR, EULAR, and British Society of Rheumatology treatment guidelines, gout flare prophylaxis is also recommended to reduce the potential for acute gout flares that can occur with the initiation of ULTs ([Khanna 2012](#), [Zhang 2006](#)). In this study, subjects are required to take colchicine for gout flare prophylaxis from the Baseline Visit (1 day before starting IP) through their Month 6 study visit as long as they are on IP during this period ([Khanna 2012](#)). Subjects who have a documented intolerance or allergy to colchicine or who are taking a concomitant medication contraindicated for use with colchicine are permitted to take low-dose oral corticosteroids (ie, defined as ≤ 10 mg/day of prednisone, or prednisolone, or their equivalent) for a short course, such as through the Month 3 study visit. Nonsteroidal anti-inflammatory drugs (NSAIDs) for gout flare prophylaxis will not be permitted due to the potential for nephrotoxicity.

The primary objective of this study is to better understand the safety profile of lesinurad 200 mg in combination with an XOI in subjects with moderate renal impairment, focusing on renal safety. Safety endpoints include analyses of absolute and percent change from Baseline in renal function with treatment over a 24 month period and the incidence of renal-related, kidney stone, and CV AEs. The key efficacy endpoint is the proportion of subjects achieving sUA levels of < 6.0 mg/dL at Month 6. This sUA target is below the saturation point for monosodium urate and is recommended by the current ACR and EULAR treatment guidelines for ULTs to treat hyperuricemia in order to promote crystal dissolution and prevent crystal formation ([Richette 2014](#), [Khanna 2012](#), [Jordan 2007](#)).

2. STUDY OBJECTIVES

The objectives of this study are as follows:

Primary Objective:

- To evaluate the safety over 24 months of lesinurad 200 mg once daily (qd) when used in combination with a xanthine oxidase inhibitor (XOI), compared with XOI alone, in subjects with gout and moderate renal impairment (estimated creatinine clearance 30 to <60 mL/min) who have not reached target serum uric acid (sUA) levels on an XOI alone.

Efficacy Objective:

- To evaluate the efficacy over 24 months of lesinurad 200 mg qd in combination with an XOI, compared with XOI alone, in subjects with gout and moderate renal impairment who have not reached target sUA levels on an XOI alone.

3. INVESTIGATIONAL PLAN

3.1. Overall Study Design and Plan

This study will be conducted in up to approximately 300 sites in North America and Europe. Subjects with gout, moderate renal impairment, and who are not at target sUA of <6.0 mg/dL on XOI alone will be enrolled. The study will include an approximate 1-month Screening Period, a 24-month Double-Blind Treatment Period, and a 1-month post-treatment Follow-Up Period.

To be eligible for the study, subjects must be on a stable, medically appropriate dose of XOI as their sole ULT indicated for the treatment of gout for at least 4 weeks prior to Screening and throughout the Screening Period. Investigators should have followed the treatment guidelines to determine the medically appropriate dose of XOI. During the Screening Period, subjects will complete 2 Screening Visits: Screening Visit 1 (approximately 1 month before the Baseline Visit) and Screening Visit 2 (3 weeks after Screening Visit 1 [± 3 days]). To be eligible for the study, estimated creatinine clearance (eCrCl; calculated by the Cockcroft-Gault formula using ideal body weight) must be 25.0 to ≤ 65.0 mL/min at each Screening Visit and the average eCrCl of both Screening Visits must be 30.0 to <60.0 mL/min, which is the Screening eCrCl. Additionally, subjects must have an sUA level ≥ 6.0 mg/dL (387 $\mu\text{mol/L}$) at both Screening Visits.

Subjects who qualify for the study will be randomized at the Baseline Visit (4 to 7 days after Screening Visit 2) in a double-blind fashion to 1 of 2 treatment groups in a 1:1 ratio:

- LESU + XOI: lesinurad 200 mg qd and XOI.
- PBO + XOI: placebo qd and XOI.

Randomization will be stratified by the Screening eCrCl subgroup (30.0 to <45.0 mL/min or 45.0 to <60.0 mL/min), Baseline measurable target tophus status (present/absent), and type of XOI (allopurinol or febuxostat). This study will enroll approximately 50% of subjects with eCrCl 30.0 to <45.0 mL/min and approximately 50% with eCrCl 45.0 to <60.0 mL/min. When the maximum number of subjects in one of the eCrCl subgroups has been reached, subsequent enrollment will be limited to subjects in the other eCrCl subgroup. There are no limitations on the number of subjects enrolled by type of XOI or Baseline tophus status.

After randomization at Baseline, subjects will be dispensed IP (lesinurad or placebo) and study-supplied XOI at the same dose as the subject's prescribed stable dose, which they will start the next day (Day 1). Subjects will take IP qd in combination with their stable dose of XOI for up to 24 months. Gout flare prophylaxis with colchicine is required from the Baseline Visit through the Month 6 study visit, while still on IP. Subjects who have a documented intolerance or allergy to colchicine or who are taking a concomitant medication contraindicated for use with colchicine (eg, P-glycoprotein [P-gp] or strong cytochrome P450 [CYP]3A4 inhibitors) are permitted to take low-dose oral corticosteroids (≤ 10 mg/day of prednisone, or prednisolone, or their equivalent) for a short course, such as through the Month 3 study visit. The use of NSAIDs for gout flare prophylaxis is not permitted. More information on gout flare prophylaxis dosing is provided in [Section 5.3](#). In order to maintain the blind, post-Baseline sUA levels will remain

blinded to the sites, subjects, and study team; additional blinding information is provided in [Section 5.5](#).

After initiating IP, subjects will return to the study site at Month 1 (± 7 days), at Month 3 (± 7 days), and every 3 months (± 7 days) thereafter until the end of the Treatment Period (Month 24 ± 7 days). Safety assessments will include an evaluation of AEs with particular focus on renal and CV events, clinical laboratory parameters (hematology, serum chemistry, urinalysis), and vital signs. Efficacy assessments will be based on an evaluation of sUA levels with assessments on tophus measurements, patient-reported outcomes, and gout flares.

[figure not shown]
Subjects who permanently discontinue IP early should complete an End of Treatment Visit as soon as possible, followed by a Post-End of Treatment Visit 1 month after the End of Treatment Visit where all AEs must be recorded. Subjects should then continue on study (and may remain on their study-supplied XO) and follow the protocol-defined schedule of events, including the End of Study Visit.

All subjects who complete the Treatment Period or who plan to withdraw early from the study should complete the End of Study Visit approximately 1 month after IP is completed or discontinued.

An independent Data Monitoring Committee (IDMC) will be appointed by the Sponsor and will evaluate the safety data periodically to protect subject welfare and to identify potential safety signals. An independent Cardiovascular Endpoints Adjudication Committee (CEAC) will routinely assess all SAEs and other prospectively-defined AEs for CV related events. An independent Renal Events Adjudication Committee (REAC) will routinely evaluate and categorize all serious prospectively-defined renal-related and kidney stone AEs, and any additional SAEs deemed by the REAC Chair to be relevant for adjudication, and will assess the likelihood that potential contributing factors, including IP, contributed to the event.

[Figure 1](#) presents the overall study design scheme. [Figure 2](#) presents the laboratory eligibility criteria during the Screening Period.

Figure 1: Overview of Study Design Scheme

Abbreviations: EOS, End of Study; EOT, End of Treatment; qd, once daily; SV, Screening Visit; wk, week; XO1, xanthine oxidase inhibitor.

Note: A clinical month is considered to be 28 days.

^a Subjects will enter the study on a stable, medically appropriate dose of XO1 (allopurinol or febuxostat) for at least 4 weeks prior to Screening and throughout the Screening Period and will continue this dose (study-supplied after Baseline) throughout the study.

[figure not shown]
^b Gout flare prophylaxis, colchicine, will be taken through the Month 6 study visit as tolerated. If low-dose corticosteroids are used as gout flare prophylaxis, the course may be through the Month 3 study visit.

^c Subjects will start investigational product (lesinurad/placebo) and study-supplied XO1 on Day 1 (1 day after the Baseline Visit). Day 1 is not a study visit. Gout flare prophylaxis may be started at the Baseline Visit.

^d Subjects who permanently discontinue lesinurad/placebo early should complete an EOT Visit as soon as possible followed by a Post-End of Treatment Visit 1 month later. Subjects should then continue to follow the protocol-defined schedule of events.

^e Subjects who complete the study or plan to withdraw from the study early should complete an EOS Visit approximately 28 days after study treatment completion or discontinuation.

Figure 2: Laboratory Eligibility Requirements

Abbreviations: BL, Baseline; eCrCl estimated creatinine clearance; IP, investigational product; sUA, serum uric acid; SV, Screening Visit; XO1, xanthine oxidase inhibitor.

3.2. Study Endpoints

3.2.1. Safety Endpoints

- Absolute and percent change from Baseline in eCrCl to Month 24.
- Absolute and percent change from Baseline in eCrCl over the study period, including the last value on and off treatment.
- Incidence of sCr elevations ($\geq 1.5 \times$ Baseline) over the study period.
- Incidence of subjects meeting criteria (eg, based on sCr or eCrCl criteria) for treatment discontinuations over the study period.
- Incidence of renal-related and kidney stone TEAEs and SAEs.
- Prevalence of contributing factors to renal SAEs as adjudicated by the REAC.
- Incidence of CEAC-adjudicated MACE (CV death, nonfatal myocardial infarction, and nonfatal stroke).
- Incidence of CEAC-adjudicated MACE or hospitalization for unstable angina (MACE+).

3.2.2. Efficacy Endpoints

- Key efficacy endpoint: Proportion of subjects who achieve sUA < 6.0 mg/dL at Month 6.
- Absolute and percent change from Baseline in sUA at each visit.
- Proportions of subjects who achieve sUA < 6.0 mg/dL at each visit.

The efficacy endpoints will be repeated by Baseline eCrCl subgroups.

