8.1.3. Baseline Visit (4 to 7 Days After Screening Visit 2)

The following procedures and assessments will be performed:

- Review gout flare history prior to Screening and during the Screening period.
- Confirm continued eligibility.
- Record complete medical history.
- Record concomitant medications.
- Administer patient report outcome assessments.
- Take vital signs.
- Record 12-lead ECG.
- Assess AEs (pretreatment).
- Perform physical examination.
- Identify and measure target tophi.
- Collect blood sample for hematology.
- Collect blood sample for the following serum chemistry analyses:
 - Analytes 1.
 - Analytes 2.
 - Analytes 3.

- Collect blood sample for plasma biomarkers.
- Collect urine sample for the following analyses:
 - Urinalysis.
 - Protein-creatinine ratio.
 - Urine biomarkers.
- Assess compliance with prescription XOI and discontinue.
- Randomize subject.
- Dispense IP (lesinurad or placebo), XOI, and colchicine (if applicable).

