9.1. General Considerations

All subjects will be randomized to either lesinurad 200 mg or matching placebo in combination with an XOI in a 1:1 ratio and stratified by the following stratification factors:

- Screening eCrCl: the average eCrCl of Screening Visit 1 and Screening Visit 2 (30.0 to <45.0 mL/min or 45.0 to <60.0 mL/min).
- Baseline measurable target tophus status: present or absent.
- Type of XOI: allopurinol or febuxostat.

This study will enroll approximately 50% of subjects with eCrCl 30.0 to <45.0 mL/min and approximately 50% with eCrCl 45.0 to <60.0 mL/min. There is no planned sample size requirement on the number of subjects enrolled by type of XOI or Baseline tophus status. However, a stratification variable (eg, Baseline measurable target tophus status [present/absent]) may be dropped from the stratified analysis (eg, mixed model repeated measures [MMRM] or Cochran Mantel Haenszel [CMH]) if the number of subjects in any stratum is very low (eg, <10% of total subjects). The decision to drop a stratification variable will be made prior to database lock and will be documented in the SAP.

All safety and efficacy data will be listed and summarized by treatment group.

Baseline is defined as the last observed measurement prior to the first dose of IP, unless otherwise specified.

Descriptive statistics will consist of the number of subjects (n), mean, standard deviation (SD), median, minimum, and maximum for continuous variables, and counts and percentages for categorical variables.

Unless otherwise specified, all confidence intervals (CIs) will be calculated at the 95% level and all hypothesis tests will be performed at the 0.05 level. All analyses including summaries and listings will be performed using SAS[®] software version 9.1 or higher.

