9.4.3. Efficacy Analyses

Efficacy data will be summarized and analyzed in the ITT population.

The key sUA efficacy endpoint (proportion of subjects with sUA <6.0 mg/dL at Month 6) will be summarized descriptively by treatment group and a comparison of the response rates will be presented using the CMH test statistic, stratified by type of XOI, Baseline measurable target tophus status (present/absent), and Screening eCrCl (30.0 to <45.0 mL/min or 45.0 to <60.0 mL/min), as appropriate as stated in [Section 9.1](#). Results will be expressed as proportions, corresponding adjusted 95% CI of the difference between response rates, and p-values. Subjects who are missing their Month 6 sUA results will be analyzed as non-responders.

The LESU + XOI group will be deemed superior compared with the PBO + XOI group if there is sufficient statistical evidence to reject the following null hypothesis:

H₀: $p_1 = p_2$ ie, no evidence that the proportion of subjects achieving an sUA response by Month 6 in the LESU + XOI group is different from the PBO + XOI group.

and in favor of the alternative hypothesis:

H₁: $p_1 \neq p_2$ ie, the proportion of subjects achieving an sUA response by Month 6 in the LESU + XOI group is different from the PBO + XOI group.

The key efficacy endpoint will be tested in the overall study population as well as the subset of subjects whose Screening eCrCl is 30.0 to <45.0 mL/min. To account for multiplicity, a hierarchical testing procedure will be performed to preserve an overall alpha at 0.05 level. First, the null hypothesis for the key efficacy endpoint will be tested in the overall population at an alpha level of 0.05. If the null hypothesis is not rejected, the testing will be stopped. Otherwise, the endpoint will then be tested in the subset of subjects whose screening eCrCl is 30.0 to <45.0 mL/min at an alpha level of 0.05.

Sensitivity analyses (eg, observed cases or other imputation approaches) will be explored to assess the impact of missing data (details provided in the SAP).

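### Section 3.2.2 repeats efficacy by Baseline eCrCl subgroups, while randomization, enrolment caps, power and the hierarchical test all use Screening eCrCl

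*Combined protocol and SAP*

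**What the plan says.** The endpoint section closes its efficacy list with: "The efficacy endpoints will be repeated by Baseline eCrCl subgroups" (Section 3.2.2). It gives no cut points. Section 9.4.3, which sets out the efficacy analyses, does not describe this repeat.

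Two different eCrCl variables are defined:

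- **Baseline.** "Baseline is defined as the last observed measurement prior to the first dose of IP, unless otherwise specified" (Section 9.1). Section 3.2.2 does not specify otherwise. A creatinine sample is drawn at the Baseline Visit, 4 to 7 days after Screening Visit 2 (Section 8.1.3), so Baseline eCrCl is normally that single value.
- **Screening.** "the average eCrCl of both Screening Visits must be 30.0 to <60.0 mL/min, which is the Screening eCrCl" (Section 3.1). The eligibility range is set on this mean, with wider limits of 25.0 to 65.0 on each screening value. No range is set for the Baseline value.

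Screening eCrCl is the variable used in the rest of the design: the randomization strata (Sections 3.1, 5.4, 9.1), the enrolment cap by stratification subgroup (Sections 3.1 and 4.3), the per-stratum power statement (Section 9.2) and the second hierarchical test in 30.0 to <45.0 mL/min (Section 9.4.3). The CMH comparison of the key endpoint is "stratified by type of XOI, Baseline measurable target tophus status (present/absent), and Screening eCrCl" (Section 9.4.3).

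**The concern.** The key endpoint, sUA <6.0 mg/dL at Month 6, is one of the efficacy endpoints to be repeated. The report could therefore carry two lower-eCrCl results for the same endpoint: one from the hierarchical test by Screening eCrCl, and one from the subgroup repeat by Baseline eCrCl, in partly different subjects. The by-visit response and sUA-change results by subgroup would likewise not describe the subset tested under alpha control.

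This matters because the lower stratum is a main reason for the trial. Section 1.3 reports only 84 Phase 3 subjects with eCrCl 30 to <45 mL/min, and half of this trial is reserved for that range. With no cut points stated, a programmer would also have to decide what to do with Baseline values below 30 or at 60 and above.

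**Working it through.** **1. The plan's own figures.** Inputs from Section 9.2: 20% vs 35%, two-sided alpha 0.05, 300 per arm overall. About 150 per arm per stratum follows from the 50/50 enrolment. With mean rate 0.275,

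power = Φ{[0.15 − 1.96·√(2·0.275·0.725/n)] / √[(0.20·0.80 + 0.35·0.65)/n]}

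- n = 300: (0.15 − 0.0715)/0.0359 = 2.19, power 98.6% (stated >90%).
- n = 150: (0.15 − 0.1011)/0.0508 = 0.96, power 83.2% (stated >80%).

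Both reproduce, and both refer to Screening strata.

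**2. How far the two variables differ.** By the Section 6.9.1 formula, eCrCl is inversely proportional to creatinine. Ideal weight is fixed by screening height and age hardly moves, so the within-subject creatinine CV carries over to eCrCl. The mean of two visits has error CV/√2 and the single Baseline value has error CV. The SD of their difference at 45 mL/min is therefore about 45·CV·√1.5: 1.7 mL/min at CV 3%, 2.8 at 5% and 5.5 at 10%. Subjects that close to 45 are liable to change side.

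**3. Share of subjects moved.** The documents give neither a short-term CV nor an eCrCl distribution, so both are assumptions. The simulation took true eCrCl as N(45, 10) with three lognormal measurements, applied the Section 3.1 screening limits, and weighted the Screening strata 50/50.

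| Assumed CV | Cross 45 | Outside 30 to <60 | Total if 30/45/60 apply at Baseline |
|---|---|---|---|
| 3% | 6% | 2% | 8% |
| 5% | 10% | 4% | 14% |
| 7% | 14% | 5% | 19% |
| 10% | 20% | 8% | 28% |

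Of 600 subjects, 6% to 20% is about 36 to 120, and 8% to 28% is about 48 to 168. Four other assumed shapes (uniform 20 to 75, normal 55/12, normal 45/8, rising 20 to 75) give 4% to 7% crossing at CV 3% and 15% to 22% at CV 10%. Their totals are 8% to 9% and 28% to 30%. If the Baseline subgroups are simply <45 and ≥45, only the crossing column applies.

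**4. Effect on size and power.** Movement runs in both directions and nearly cancels. Under the N(45, 10) model, a Baseline <45 subgroup averages about 300 to 307 subjects and a 30 to <45 subgroup about 290 to 296. Power for 20% vs 35% is about 82% to 84%, against 83.2% in the Screening stratum.

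**5. Effect on balance.** Take CV 10%: about 60 of 300 leave the lower stratum and about 60 enter from the upper one, each stratum being split 150:150. The variance of the LESU count is 240·0.25·(60/299) + 60·0.25·(240/299) = 24.1, SD 4.9. As a share of 300 this is 1.6 percentage points, so the LESU share lies within about 47% to 53% in 95% of trials.

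**The case against.** Four points can be made for the plan.

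- **Loose wording.** The only eCrCl subgroups with stated cut points are Screening-based, the synopsis endpoint list omits the sentence, and Section 9 defers detail to the SAP. This is possible but weak: Section 9.4.2.1 puts Screening eCrCl (as a stratification factor) and Baseline eCrCl (as a covariate) in one model, so the authors do distinguish them.
- **A Baseline subgroup is legitimate.** It is measured before dosing, and Section 1.3 describes Phase 3 consistency by Baseline renal function, so it could serve comparison with Phase 3. This stands, and is a reason to allow it as a labelled supplement.
- **Confirmatory results are untouched.** This also stands. The hierarchical test is fixed on Screening eCrCl, and no hypothesis test is attached to the Baseline repeats. A reader might infer that alpha control or the stated power is compromised; the documents do not support that.
- **Balance and size survive.** A reader might infer that the subgroups lose 1:1 allocation or the planned 150 per arm. Treatment cannot affect a pre-dose value, so allocation stays 1:1 in expectation, and steps 4 and 5 show little change. Only the exact balance given by stratification is lost.

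**Conclusion.** The mismatch is in the text and should be corrected. As written, the supportive subgroup results would not describe the same subjects as the alpha-controlled 30.0 to <45.0 mL/min subset or the randomized strata. The harm is to consistency and interpretation; validity is not at stake.

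The size rests on an assumed CV: about 6% to 20% of subjects cross 45 mL/min at CV 3% to 10%. A reader might infer that about one subject in five changes subgroup or has none. That needs a CV near 7% and limits of 30 and 60 at Baseline, and the documents state neither. The nearest figure in the plan, a 20% SD of percent change to Month 24 (Section 9.2), includes real change over 24 months. It gives only a loose ceiling of 20%/√2, about 14%, on the short-term CV.

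**What to change.** In Section 3.2.2, replace the reference to Baseline subgroups with *Screening eCrCl strata (30.0 to <45.0, 45.0 to <60.0 mL/min)*, and add a matching sentence to Section 9.4.3. The repeats would then use the randomized strata, about 150 per arm each, and no subject would be moved or left out.

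If a Baseline eCrCl analysis is also wanted, for example for comparison with Phase 3, state its cut points, say how values <30 or ≥60 mL/min are handled, and label it supplementary.

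The cost is a change of wording, with no effect on data collection, sample size or the confirmatory tests. The one thing given up is Baseline eCrCl as the main subgroup variable, and the supplement preserves it. The change should be settled before unblinding.
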